9.7.1. Co-primary objectives

• To determine the total health burden of RSV-associated RTI with a suspicion of involvement of the lower respiratory tract.

Incidence rates will be calculated as the number of RSV-associated RTI with a suspicion of involvement of the lower respiratory tract over the number of children-years observations, overall and by subgroups.

Descriptive statistics of the different types of healthcare utilization from all healthcare settings will be provided (proportions, duration, etc.) among RSV-associated RTI with a suspicion of involvement of the lower respiratory tract, overall and by subgroups.

• To assess the performance of the LRTI case definition and severity scale for RSV-associated cases.

Incidences rates will be calculated as the number of RSV-associated LRTI/severe LRTI as classified by the LRTI case definition and severity scale and also as classified by the comparator case definitions (WHO and Nokes, et al [Modjarrad, 2016; Nokes, 2004]), over the number of children-years observations, overall and by subgroups.

Descriptive statistics of the different types of healthcare utilization will be provided (proportions, duration, etc.) among RSV-associated LRTI/severe LRTI as classified by the LRTI case definition and severity scale and also as classified by the comparator case definitions (WHO and Nokes, *et al* [Modjarrad, 2016; Nokes, 2004]), overall and by subgroups.

Statistical analysis of agreement will be performed to compare the different case definitions of RSV-associated LRTI/severe LRTI and key healthcare utilization and health outcomes (the hospitalization status, (P) intensive care unit [ICU] attendance, clinical diagnosis of bronchiolitis or pneumonia, death) overall and by age categories.

Table 15 Comparison of two classifications for severe/Non-severe LRTI

RSV-associated cases		Classification of reference (severe/Non-severe)		
		Hospitalized	Not hospitalized	
Alternative classification (severe / Non-severe)	Severe LRTI (LRTI case definition and severity scale)	True positive (TP)	False positive (FP)	
	Non-severe LRTI (LRTI case definition and severity scale)	False negative (FN)	True Negative (TN)	

2x2 contingency tables such as Table 15 will be provided and the following measures of agreement (with 95% CI) will be calculated:

- Sensitivity: TP/ (TP+FN)
- Specificity: TN/ (TN+FP)
- Positive predictive value (PPV): TP/ (TP+FP)
- Negative predictive value (NPV): TN/ (TN+FN)

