6.4. General considerations calculations of incidence

When mentioned below in the upcoming analyses sections, analysis by subgroups will include:

- Country
- Age interval:
 - 0-5M
 - 6-11M
 - 0-11M
 - 12-23M
 - 0-23 M
- Age interval by months for the first 6 months

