6.6.2. Analysis of secondary objective: incidence of all cause respiratory disease

The analysis will be based on PPS and will be done on the first episode of all cause RTIs occurring during the age interval considered.

200150 (EPI-RSV-005 BOD)

Statistical Analysis Plan Amendment 1 Final

The incidence will be computed overall and by age category:

- 0-5 months
- 6-11 months
- 0-11 months
- 12-23 months
- 0-23 months

Incidences rates will be calculated using the same approach describe in section 11.1.1 for first episode of RTI with a suspicion of involvement of the lower respiratory tract, WHO LRTI and WHO severe LRTI and LRTI hospitalization.

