- The risk factor analysis will be done using a Cox regression model and not a Poisson regression model to be consistent with the analysis performed in clinical trials.
- The sensitivity analysis will not be performed on the total enrolled cohort.
- The analysis of the impact of changes to the symptoms and threshold levels of symptoms in the LRTI case definition and severity scale will not be done by age category

200150 (EPI-RSV-005 BOD)

Statistical Analysis Plan Amendment 1 Final

- The date of study conclusion for subjects lost to follow-up will be the date of conclusion given in the CRF and will not be derived according to number of missed visits.
- Only first episode within a given age interval is considered for the computation of incidence. The incidence of event is computed using 3 different calculation methods: incidence rate, proportion affected, and incidence proportion. See section 11.1.1 for detail of calculation
- Sub-group of analysis for birth period outside or within transmission season will not be performed. Instead, the analysis will be based on the first 6 month of subject's life, and will be done considering 2 categories: <= 3 months and > 3 months. The incidence rate of RSV associate LRTI, severe LRTI, and hospitalization will be computed by country.
- Incidence and performance of case definition analysis (measures of agreement) will be performed using exploratory case definitions in anticipation of update to WHO case definitions.
- Analyses of cord blood collection using and not using recommended procedures will not be done. Instead, descriptive statistics for cord blood collection variables and cord blood levels of RSV A and B neutralizing antibodies according to cord blood collection variables will be provided. Additional analyses will be performed to evaluate disease surveillance and protocol procedures and include summary of number and percent of surveillance contacts followed by an exam visit, the duration between surveillance contact and exam visit, and duration between nasal swap and onset of symptoms.

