11. ANNEX 1 STANDARD DATA DERIVATION RULE AND STATISTICAL METHODS

11.1. Statistical Method References

11.1.1. Computation of incidence rates

For each endpoint, the incidence rate (IR, number of episodes/endpoints per 100 personyears) will be calculated by dividing the number of subjects reporting first episode over the follow-up period by the total person-year. A 95% CI will be computed using an exact method for a Poisson variable as described below.

The person-time at risk for an event of interest (e.g. RSV-LRTI) will be calculated as the time between the date of birth and the end of the at-risk period or the earliest of the followings:

200150 (EPI-RSV-005 BOD)

Statistical Analysis Plan Amendment 1 Final

- Date of first diagnosis of event of interest (e.g. first episode of RSV-LRTI);
- Date when child reaches 2 years;
- Date of last contact (lost-to follow-up, defined as no contact by the subject's parent(s)/LAR(s) over the period of 3 planned contacts and/or 2 months and after a final attempt has been made by mail. Once this has been reached, the subject is censored at the time of last contact);
- Date of death.

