
Center	Total N =	
	n	%

N = number of subjects of total enrolled cohort

n = number of subjects enrolled for a given center

Center = GSK biologicals assigned center number

% = n/N

- 12.3. Incidence
- 12.3.1. Primary incidence analysis
- 12.3.1.1. (PO1) To determine the total health burden* of RSV-associated RTI with a suspicion of involvement of the lower respiratory tract
- Template 7 Incidence rate of first episode of [RSV RTI with suspicion of involvement of LRT, WHO RSV LRTI, WHO RSV severe LRTI, RSV hospitalization, WHO RSV LRTI hospitalization, WHO RSV severe LRTI hospitalization], by age interval overall and by country (PPS)

						95% exact Cl	
Country	Age interval (Months)	Total number of subjects	Total number of first episode	Total number of person- years	Incidence rate (100 person- years)	LL	UL
Overall	0-5						
	6-11						
	0-11						
	12-23						
	0-23						
<each country=""></each>							1

Incidence rate computed using the number of first episode as numerator and the total number of person-years over the entire follow-up as denominator

CI=confidence interval, LL, UL for incidence = Exact 95% Lower and Upper confidence limits

Template 8 Incidence rate of first episode of WHO RSV LRTI, WHO RSV severe LRTI, RSV hospitalization, by age interval – by country (PPS)

		95% exact CI						
Country	Age interval	Episodes	Total number of subjects	Total number of first episode	Total number of person- years	Incidence rate (100 person- years)	LL	UL
<each country ></each 	0-11 months	WHO RSV LRTI						
		WHO RSV severe LRTI						
		RSV hospitalization						
	12-23 months	WHO RSV LRTI						
		WHO RSV severe LRTI						
		RSV hospitalization						

Incidence rate computed using the number of first episode as numerator and the total number of person-years over the entire follow-up as denominator

CI=confidence interval, LL, UL for incidence = Exact 95% Lower and Upper confidence limits
Statistical Analysis Plan Amendment 1 Final

Template 9 Proportion affected by at least one episode of [RSV RTI with suspicion of involvement of LRT, WHO RSV LRTI, WHO RSV severe LRTI, RSV hospitalization, WHO RSV LRTI hospitalization, WHO RSV severe LRTI hospitalization] by age interval – overall and by country (PPS)

					95% e	xact Cl
Country	Age interval (Months)	Total number of subjects at birth	Total number of subjects affected	Proportion affected	LL	UL
Overall	0-5					
	6-11					
	0-11					
	12-23					
	0-23					
<each country=""></each>						

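### The person-time written for the co-primary RSV incidence rates does not match the age-interval numerator; taken literally, it makes the 6-11 and 12-23 month rates about 1.7 to 4 times too low

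*SAP*

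**What the plan says.** **Numerator.** SAP Section 9: "Only first episode within a given age interval is considered for the computation of incidence". SAP 6.4 makes age interval (0-5, 6-11, 0-11, 12-23 and 0-23 months) one of the subgroups for incidence. Template 7 in SAP 12.3.1.1 has a row for each of these; Template 8 has the two years of life.

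**Denominator, template footnotes.** Templates 7 and 8, and Template 34 for the exploratory definitions, use the "total number of person-years over the entire follow-up as denominator". Template 12 uses nearly the same wording for a rate confined to the first six months of life.

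**Denominator, SAP 11.1.1.** Person-time "will be calculated as the time between the date of birth and the end of the at-risk period", or to the earliest of several stops. These include "Date of first diagnosis of event of interest (e.g. first episode of RSV-LRTI") and "Date when child reaches 2 years", along with last contact and death. The at-risk period is not defined, and no start other than birth is given.

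**Parallel all-cause table.** SAP 6.6.2 says of those rates: "Incidences rates will be calculated using the same approach describe in section 11.1.1". The Template 15 footnote, however, restricts person-years to the age interval.

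**Protocol 9.7.1.** RSV cases are to be taken "over the number of children-years observations, overall and by subgroups"; protocol 9.5.1 lists age categories among the possible subgroups.

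**The concern.** A rate needs events and person-time from the same window. Here the events come from a 6- or 12-month window, while the time comes from birth onwards or from the whole two years. The SAP supports three different denominators for one stated method: whole follow-up, birth to the interval end, and the interval itself. Nothing written assigns the third, which is the correct one, to the RSV rates.

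Re-entry is also unsettled. Section 9 counts a first episode in each interval, so a child with an episode at 3 months can count again at 8 months. Section 11.1.1 stops that child's clock at the first diagnosis. A risk-set rule is written only for incidence proportion (11.1.4).

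These are co-primary burden results, and Section 9 prefers pooled incidence by year of life as the overall summary. Under the footnotes both yearly rates are about halved. Under 11.1.1 read to the interval end, the first year is right and only the second is about halved, so the age pattern itself depends on the programmer's reading.

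**Working it through.** **Plan's own figure.** The documents give no age-interval rate. The nearest is the protocol Table 13 row for 20 per 1000 in the first year of life, with 6 cases in 320 child-years.
- Exact limits: χ²(0.025; 12)/2/320 = 6.9 and χ²(0.975; 14)/2/320 = 40.8 per 1000.
- With design effect 1 + (160 − 1) × 0.02 = 4.18, the upper limit is 20 + 1.96 × √(4.18 × 0.020/320) × 1000 = 51.7, and the lower is cut at 0.

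Both agree with the protocol. That planning gives 320 evaluable children about one child-year each for a first-year rate, which is interval person-time.

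**Simplest bound.** With few events and no dropout, the footnote rule understates a 6-month row by 24/6 = 4 and a 12-month row by 24/12 = 2. Birth to interval end understates 6-11 months by 12/6 = 2 and 12-23 months by 24/12 = 2.

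**Inputs.**
- RSV hospitalisation rates, protocol Table 12, per 1000 child-years for 0-5, 6-11 and 12-23 months: low 16.9, 5.1, 0.4; high 44.1, 15.0, 3.7.
- RSV LRTI rates: 8 times these (protocol 9.3).
- Dropout: 20% by two years (protocol 9.3), taken as a constant hazard d = −ln(0.8)/2 = 0.112 per year (assumption); 0% as sensitivity.

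**Formulas.** Let H(t) be the cumulative event rate to age t.
- Correct person-time for [a, b): P = ∫ₐᵇ exp(−dt) · exp(−[H(t) − H(a)]) dt.
- Understatement factor: written person-time / P.
- The footnotes do not say when the clock stops, so whole follow-up was computed without a stop, stopped at first-ever episode, and stopped at first episode in the interval. Birth to interval end was computed with each of the two stops.

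**Upper LRTI rates (35.28, 12.00, 2.96 per 100 person-years), 20% dropout.** Whole follow-up per child is 1.793 years unstopped and 1.479 stopped at first-ever episode. Stopping at the first episode in the interval always falls between these.

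| Age (months) | P (years per child) | First episodes per child | Correct rate /100 PY | Footnote rule (factor) | 11.1.1 to interval end (factor) |
|---|---|---|---|---|---|
| 0-5 | 0.446 | 0.157 | 35.3 | 8.8-10.6 (3.31-4.02) | 35.3 (1.00) |
| 6-11 | 0.447 | 0.0536 | 12.0 | 3.0-3.6 (3.31-4.01) | 5.7-6.5 (1.84-2.09) |
| 0-11 | 0.820 | 0.202 | 24.7 | 11.3-13.7 (1.80-2.18) | 24.7 (1.00) |
| 12-23 | 0.834 | 0.0247 | 3.0 | 1.4-1.7 (1.77-2.15) | 1.4-1.7 (1.77-2.13) |
| 0-23 | 1.479 | 0.222 | 15.0 | 12.4-15.0 (1.00-1.21) | 15.0 (1.00) |

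**Range over all planning rates and both dropout levels.**
- Footnote rule: 0-5M 3.31-4.36; 6-11M 3.31-4.12; 0-11M 1.80-2.31; 12-23M 1.67-2.15; 0-23M 1.00-1.22.
- 11.1.1 to interval end: 6-11M 1.78-2.09; 12-23M 1.67-2.13; other rows 1.00.
- 11.1.1 to age 2: the footnote rule with the clock stopped.

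Counting only first-ever episodes does not rescue birth to interval end: the factors are then 2.01-2.19 (6-11M) and 2.00-2.25 (12-23M).

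**Re-entry.** If the start is moved to age a but the stop at first-ever diagnosis is kept, time is lost for children with an earlier episode whose later episode still counts. The rate is then too high by exp(H(a)).
- Upper LRTI, a = 6 months: exp(0.3528 × 0.5) = 1.19. a = 12 months: exp(0.1764 + 0.0600) = 1.27.
- Low hospitalisation rates: 1.01 at both ages.

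**The case against.** The strongest reply is that the intent is plain. SAP 6.4 says "analysis by subgroups will include" age intervals, SAP Table 12 lists the RSV rates by age interval, Template 7 has a person-years cell in every row, and Template 15 has the right wording. The footnotes may simply be carried over, and a whole-follow-up denominator would show in the printed person-years. I accept that interval person-time was probably meant. But those passages define rows, not a clock. Four template footnotes say otherwise, and 11.1.1, the only method text, starts at birth. Neither correct interval entry nor the re-entry rule can be read from it.

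Three limits stand.
- Factors above 4.0 arise only if the clock never stops. With the 11.1.1 stop at diagnosis the maximum is 4.0.
- The lower bound depends on the event rate. If the protocol's upper LRTI cumulative incidences (32% in year one, 17% in year two) are taken as the rates, the 12-23 month factor falls to about 1.6.
- A link to the SAP Section 7 trigger for revising the case definition is weak. Rates under the sponsor's definition are no longer computed, and the literature rates in protocol Table 12 are hospitalisation rates. The conclusion does not rest on it.

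Kaplan-Meier estimates and incidence proportions are unaffected.

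**Conclusion.** The concern holds: the rule is wrong as written for co-primary rates and should be corrected before the analysis is programmed. No written rule for the RSV rates gives a correct 6-11 or 12-23 month value, and under the footnotes the 0-5 and 0-11 month rows are wrong as well. The size is conditional on literal reading, the protocol's planning rates and evenly accruing dropout: about 3.3 to 4 for the six-month rows under the footnotes, and about 1.7 to 2 for 12-23 months under either reading. The exact Poisson interval uses the same person-years, so it moves with the estimate and gives no warning.

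**What to change.** - **SAP 11.1.1.** For interval [a, b), count person-time from age a, for children still followed at a, to the earliest of first episode in that interval, age b, last contact or death. State that a child with an episode in an earlier interval re-enters the risk set, as Section 9 implies, and reword the stop at first diagnosis to match.
- **Footnotes.** In Templates 7, 8 and 34, refer to person-years within the age interval, as Template 15 does. In Template 12, refer to the first six months of life.

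Cost: SAP wording and one person-time derivation; no new data.

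Two neighbouring points can be settled in the same amendment. Protocol 9.5.1 asks for a design-effect-adjusted interval beside the exact one; the SAP omits it and Section 9 does not list the omission, so restore it (one added column, wider intervals) or justify its removal. The Template 35 footnote divides proportion affected by subjects at birth, whereas 11.1.3 uses subjects at the start of the interval.

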12.3.1.2. Kaplan Meier analysis

Template 13 Cumulative probability of observing first episode of [RSV-RTI with suspicion of involvement of LRTI, WHO RSV LRTI, WHO RSV severe LRTI, RSV hospitalization, WHO RSV LRTI hospitalization, WHO RSV severe LRTI hospitalization] at the end of 2 year follow-up period– overall and by country (PPS)

Country	Timepoint (Month of Age)	N	n	Cumulative probability of the first episode	LL	UL	median	Q1	Q2
Overall	6								
	12								
	24								
<each country=""></each>	6								
	12								
	24								

Cumulative probability at the end of follow-up

N = total number of subjects

n = number of subjects with first episode reported

LL, UL for percentage = Exact 95% Lower and Upper confidence limits

Q1, Q3 = first and third quartiles

Template 14 Cumulative probability of observing first episode of WHO RSV LRTI in subjects at the end of 2 year follow-up period– by country (PPS)

NA

12.3.2. Secondary incidence analysis

12.3.2.1. (SO1) To determine the total health burden of non-RSV-associated RTI with a suspicion of involvement of the lower respiratory tract

Template 15 Incidence rate of first episode of [RTI with suspicion of involvement of LRT (all cause), WHO LTRI (all cause), WHO severe LRTI (all cause)], by age interval – overall and by country (PPS)

						95%	exact CI
Country	Age interval (Months)	Total number of subjects	Total number of first episode (all cause)	Total number of person- years	Incidence rate (100 person- years)	LL	UL
Overall	0-5						
	6-11						
	0-11						
	12-23						
	0-23						
<each country=""></each>							

Incidence rate computed using the number of first episode (all cause) as numerator and the total number of personyears over the age interval as denominator

CI=confidence interval, LL, UL for incidence = Exact 95% Lower and Upper confidence limits 95% CI computed using exact method for first episode incidence

Template 16 Monthly distribution of WHO RSV LRTI – by country (PPS)

	AR (N=)	BD	(N=)	CA	A (N=)	FI	(N=)	HN	(N=)	SA	(N=)	Tł	H (N=)	US	(N=)
Calendar Month	n	%	Ν	%	n	%	n	%	n	%	n	%	n	%	n	%
January																
February																
March																
April																
Мау																
June																
July																
August																
September																
October																
November																
December																

N=number of WHO RSV LRTI episode for each country

n (%) = total number and percent of WHO RSV LRTI episodes for each month

AR = Argentina

BD = Bangladesh

- CA = Canada
- FI = Finland

HN = Honduras

SA = South Africa

TH = Thailand

US = US

- 12.3.3. Tertiary incidence analysis
- 12.3.3.1. (TO5) To assess the impact of potential RSV risk factors (e.g. complications at birth, family history of respiratory disease, living environment and household composition, breast feeding, passive smoking, day care attendance) on the incidence and severity of RSV-associated LRTI.
- Template 17 Potential risk factors for first [WHO RSV LRTI WHO RSV severe LRTI] episode, evaluated in [Univariate – Multivariate] Cox model analysis for first [WHO RSV LRTI – WHO RSV severe LRTI] episode, over the 2 year follow-up period (PPS)

Characteristics	Category	Number of Observations		Hazard		Global n-
		model	Event	(95% CI)	p-value	value
RSV-A maternal antibodies levels in cord blood	Seronegative					
	Seropositive					
	Missing					
RSV-B maternal antibodies levels in cord blood	Seronegative					
	Seropositive					
	Missing					
RSV-A maternal antibodies levels in cord blood	Q1 (min - max)					
	Q2 (min - max)					
	Q3 (min - max)					
	Q4 (min - max)					
RSV-B maternal antibodies levels in cord blood	Q1 (min - max)					
	Q2 (min - max)					
	Q3 (min - max)					
	Q4 (min - max)					
RSV-A maternal antibodies levels in cord blood	Continuous					
RSV-B maternal antibodies levels in cord blood	Continuous					
Country	Argentina					
	Missing					
Gender	Female					
	Male					
	Missing					
	Within transmission					
Time of birth	season			ļ		
	Outside transmission					
	season					

200150 (EPI-RSV-005 BOD)

		Statistic	al Ana	vsis Plar	1 Amendme	nt 1 Final
Characteristics	Category	Number of Observations Used in the model	Event	Hazard ratio (95% Cl)	p-value	Global p- value
Gestational age at birth	<= 36 weeks					
	>36 weeks					
Birth weight	< 2.5 kg					
	>= 2.5 kg					
Apgar at 5 mins of age	0-3					
	4 – 6					
	>= 7					
	Missing					
First degree relative with FH of	Yes					
asthma	No					
	Missing					
Highest education level of the	Yes					
mother: Higher education /	No					
university	Missing					
Highest education level of the	Yes					
father: Higher education /	No					
university	Missing					
Number of people living in the	1-3					
household at Month 3	4-6					
	>=7					
Number of other children (<18	0					
years old) living in the	1-2					
household at Month 3	>=3					
Subject in regular close contact	Yes					
with toddlers at Month 3	No					
	Missing					
The child live in a surrounding	Yes					
where people smoke daily at	No					
Month 3	Missing					
Breast feeding*	Yes					
, č	No					
	Missing					

Hazard ratio (95% CI) = Hazard ratio and 95% confidence intervals

RSV-A / RSV-B seronegative samples are defined as samples with RSV-A / RSV-B maternal antibodies levels in cord blood < LLOQ

RSV-A / RSV-B seropositive samples are defined as samples with RSV-A / RSV-B maternal antibodies levels in cord blood >= LLOQ

* Time-varying covariates :

- Number of observations used in the model = Number of observations which appeared at least once in the followup period. One observation can be counted in several modalities.

- Event = The number of events corresponds to the value recorded at the most recent visit before the endpoint.

12.4. Primary health care utilization analysis

12.4.1. (PO1) To determine the total health burden* of RSV-associated RTI with a suspicion of involvement of the lower respiratory tract

Template 18 Number and percentage of healthcare utilization (supplementary to care provided by study sites) for all episodes of [WHO RSV LRTI, WHO RSV severe LRTI], by age interval [overall, in <each country>] (PPS)

Age interval (Months)	Characteristic	Ν	n	%
0-5	Outpatient visit			
	Emergency room visit			
	Inpatient Admission- Non-Intensive Care			
	Inpatient Admission-with intensive			
	care			
	No consultation other than site clinic			
	Other			
6-11				
0-11				
12-23				
0-23				

N = total number of episodes for the age interval considered

n/% = number / percentage of episodes in a given category with the most intense level of care utilized

Template 19 Frequency of type of caregiver and number of days care utilized per caregiver for episodes of [WHO RSV LRTI, WHO RSV severe LRTI], all episodes considered, by age interval [overall, in <each country>] (PPS)

				Number of days care per caregiver *							
Age interval (Months)	Characteristics	N	n (%)	Mean	SD	Median	Min	Max			
0-5	Usual care giver or another person took care of the child without missing work										
	A person had to stay home specifically because of the illness instead of going at work										
	A person was hired to care for the child specifically because of the illness										
6-11											
0-11											
12-23											
0-23											

N = number of episodes for the age interval considered

n/% = number of episodes for which a caregiver of a given category is provided

SD = Standard deviation

*An event will be taken into account for the calculation of the duration only if type of utilization is reported for that event. The denominator is the n.

